Section 7.9.9 Vaccine IgG (optional)	The following vaccinations were removed from the list of those allowed during the study: measles (alone or in combination), or shingles (varicella zoster virus).	These are live vaccines and are therefore not permitted during the study.

Section # and Name	Description of Change	Brief Rationale
	Clarified the optional collection of vaccine-specific IgG samples applies to participants who have received at least 6 weeks of rilzabrutinib or placebo at the time of scheduled vaccination and is applicable to the blinded treatment and open label periods and long-term extension.	Clarified who the optional collection of IgG samples is intended for.
Section 7.9.10 Immune Thrombocytopenia (ITP) Assessment Tools (IBLS, ITP-PAQ, ITP-KIT)	Added a paragraph describing intention of ITP treatments and real-world evidence of the burden of fatigue in patients with ITP.	To provide a rationale for promoting fatigue assessment from an exploratory to a key secondary efficacy endpoint.
Section 7.9.15 Use of biological samples and data for future research	New section added comprising Sanofi template standard language that explains Sponsor's intent to store biological samples for research purposes from consenting participants.	Clarification and consistency with template requirements
Section 7.9.16 Overdose, medication errors, misuses or abuses of medicinal product	New section added to provide definition and instruction for reporting of overdoses, medication errors, misuses or abuses of medicinal product.	EU CTR requirement
Section 9.3.9 Adverse Events (AEs), Serious Adverse Events (SAEs) and Other Safety Reporting	Revised instructions for AE reporting: "The Investigator and any qualified designees are responsible for detecting, documenting, and recording events reported by the participant (or, when appropriate, by a caregiver, surrogate, or the participant's legally authorized representative) that meet the definition of an AE or SAE and remain responsible for following up AEs, particularly those that are serious, considered related to the study intervention or study procedures, or that caused the participant to discontinue the study intervention or study (see Section 7.5).	Clarification and consistency with template requirements
Section 9.3.9.5 Pregnancy	Specified that only pregnancies reported after the first dose of the IMP, will be recorded by the Investigator and submitted to the Sponsor within 24 hours of learning of the pregnancy. Revised the timeframe of collection of details of all pregnancies from 7 days to 28 days after the last dose of study intervention: "Details of all pregnancies will be collected after the start of study intervention and until 28 days after the last dose of study intervention." Added the below text: "While pregnancy itself is not considered to be an AE or SAE, any pregnancy complication or elective termination of a pregnancy for medical reasons will be reported as an AE or SAE."	Clarification to align with the SoA and Sanofi template requirements.
Section 9.3.9.6 Adverse Events of Special Interest	The "symptomatic overdose with IMP" qualifier was updated to include both serious and nonserious overdoses. Specified the immediate notification timeframe to be within 24 hours.	Clarification

Section # and Name	Description of Change	Brief Rationale
	The following text was revised: Pregnancy of a female participant entered in a study and received at least one dose of the IMP as well as pregnancy occurring in a female partner of a male participant entered in a study with IMP.	
Section 12.2 Informed Consent	Added: Participants enrolled into the pediatric portion of the trial will still be considered as part of the pediatric group with all the planned assessments when they turn 18 years old. They should be re-consented with an adult consent when they become an adult per country-specific requirements.	Clarification
Appendix 10: Country-Specific Requirements	Added Appendix 10.6 Italy country-specific requirements: "For pediatric participants (10 to <18 years old) enrolled in Italy, eGFR will be calculated using the Bedside Schwartz Equation." Added Appendix 10.7 to 1) describe primary and key secondary endpoints specific to the EU (EEA countries) and the UK, 2) allow inclusion of children ≥10 to <18 years of age (EU [EEA] countries only) and 3 specify a body weight lower limit for pediatric participants.	Country-specific requirement Added to describe primary and secondary endpoints specific to the region and to specify new agreement with RA (EMA) to include pediatric participants ≥10 to <18 years (previously adolescents ≥12 years to <18 years).
Appendix 11: Protocol Amendment History	This entire section was updated with the country specific protocol amendments summary of changes tables.	Changes made to comply with Sanofi standards.
Appendix 11: Protocol Amendment History	This entire section was updated with the Amended Clinical Trial Protocol 02 summary of changes table.	Changes made to comply with Sanofi standards.
Appendix 12.3 Recording and follow-up of AE and/or SAE	Assessment of Intensity definitions modified to reflect NCI-CTCAE grading system.	Consistency with grading definitions in Section 9.3.3
Appendix 14: Patient Medication Diary	"Blank Patient Medication Diary" added to the appendices.	Added for reference.
Appendix 15: Liver Safety: Suggested Actions and Follow-up Assessments	Liver safety follow-up guidelines added.	Added to provide guidance on actions and follow-up assessments for ALT increase.
Throughout	1) The term "patient" was revised to "participant". 2) The term "caplet" was replaced with "tablet". 3) In most instances the term adolescent was replaced with pediatric. The term adolescent was retained in the protocol title.	1) To reflect common terminology in the template, 2) To correct naming of the formulation and 3) To reflect that participants 10 to <12 years may be enrolled in the EU (EEA countries).

In addition, other minor editorial changes (eg, grammatical, stylistic, references, and minor typographical error corrections) were implemented throughout the protocol.

Amended Clinical Trial Protocol 04 (24 July 2023)

This amended clinical trial protocol 04 (Amendment 04) is considered to be substantial based on the criteria set forth in Article 10(a) of Directive 2001/20/EC of the European Parliament and the Council of the European Union.

OVERALL RATIONALE FOR THE AMENDMENT

The primary reasons for this amendment are to:

- Update the 2-sided significance level from 0.01 to 0.05 for the hypothesis testing of the primary efficacy end point.
- Clarify distinct durations of participation in the long-term extension (LTE) for the adult and pediatric populations.

Protocol amendment summary of changes table

Section # and Name	Description of Change	Brief Rationale
Title Page, Protocol Amendment Summary of Changes, and headers throughout	Amendment number has been revised to "04".	Administrative change to comply with Sanofi standard format.
Protocol Amendment Summary of Changes: Document History; Appendix 11: Protocol Amendment History	Expanded the table to include previous country-specific protocol amendments and added the relevant changes to the protocol amendment history in Appendix 11.	To comply with the Sanofi template.
Section 1 Synopsis: Sample size and Primary Efficacy Analysis; Section 10.1: Determination of Sample Size; Section 10.3.9: Primary Efficacy Analysis; Section 16 Appendix 10.7: EU (EEA Countries) and UK-specific Requirements	Updated the 2-sided significance level from 0.01 to 0.05 for the hypothesis testing (ie, Cochran-Mantel-Haenszel test) of the primary efficacy end point.	To align with health authority common standard, in response to the feedback received from health authority.
Section 1 Synopsis: Sample size, and Section 10.1 Determination of Sample Size	Updated the study power from 86% to 95% to reflect the update of the 2-sided significance level from 0.01 to 0.05.	Revised to reflect the impact of changing the 2-sided significance level from 0.01 to 0.05 on the study power.
	In the following sentence "up to" has been added before "30 participants": "The pediatric sample size of up to 30 participants (20 participants on rilzabrutinib and 10 participants on placebo) was determined based on clinical practice and is adequate to descriptively describe the safety and efficacy in pediatric participants."	To clarify that 30 participants is the maximum number of pediatric participants planned to be enrolled.

Section # and Name	Description of Change	Brief Rationale
Section 1 Synopsis: Duration of Study Participation; Section 4.1: Duration of Study Participation	Revised text to specify that: For adult participants, the maximum duration of the long-term extension (LTE) period will be 12 months from the date of the last adult participant to enter the LTE. For pediatric participants, the maximum duration of the LTE period will be 12 months from the date of the last pediatric participant to enter the LTE.	To clarify the duration of participation in the LTE separately for adults and pediatrics. Due to low enrollment rate of pediatric population compared to adults, last participant in (LPI) of pediatrics expected to occur much later than LPI of adults.
Section 1 Synopsis: Table 1 (Schedule of assessments-Blinded Treatment Period), footnote d, Table 2 (Schedule of assessments-Open Label Period), footnote b, and Table 3 (Schedule of assessments-Long-Term Extension Period), footnote b; Sections 4.1.2: Blinded Treatment Period (Weeks 1 to 25); Section 4.1.3: Open Label Period (Weeks 25 to 53); Section 4.1.4: End of Study Visit (Four Weeks post last dose of study drug); Section 4.1.5: Long-Term Extension (LTE); Section 7.9.2: Physical Examination	Added cross references to Section 16 Appendix 10.6, Italy-specific requirement for details concerning Tanner staging in pediatric participants.	Health authority requirement to assess pubertal status in pediatric participants.
Section 1 Synopsis: Table 1 - Schedule of Assessments-Blinded Treatment Period	Added cross reference in footnote b to Figure 1, Decision tree for assessing response at Week 13 for details on calculating baseline platelet count.	To clarify how to calculate platelet count at baseline.
Section 1 Synopsis: Investigational plan; Section 4 Study Design	Updated the following text on calculating baseline platelet count: "The baseline value of platelet count is defined as the average of all the participant's Predose platelet counts (Screening and Study Day 1)."	To clarify how to calculate platelet count at baseline.
Section 4 Study Design	Added a footnote for Figure 1 on calculating baseline platelet count as below: "The baseline value of platelet count is defined as the average of all the participant's Predose platelet counts (Screening and Study Day 1). In case of availability of 3 platelet counts, the baseline platelet count will be the average of the 2 qualifying platelet counts during Screening and within 14 days before the first dose and the platelet count at Week 1 (Study Day 1). In case the second qualifying platelet count is collected at the Study Day 1 prior to the first dose, the baseline platelet count will be the average of the 2 qualifying platelet counts."	

Section # and Name	Description of Change	Brief Rationale
Section 1 Synopsis: Inclusion criteria #3 Section 5.1: Inclusion Criteria # 3 Section 16 Appendix 10: Country -Specific Requirements, 10.7 EU (EEA countries) and UK-specific requirements	For the following sentence, the comma is removed after "screening period" and a comma is added before the word "within": "An average of 2 platelet counts at least 5 days apart of <30,000/ μ L during the screening period and no single platelet count >35,000/ μ L, within 14 days prior to the first dose of study drug"	To clarify that both the qualifying platelet counts as well as the criterion of "no single platelet count >35,000/ μ L" should be evaluated within 14 days prior to the first dose of the study drug.
Section 1 Synopsis: Exclusion criteria #22 Section 5.2: Exclusion Criteria # 22	The following text has been added: "known allergy to any of the study medication, their analogues, or excipients in the various formulations of any agent (please see Section 6.1.1 for information on excipients)"	To exclude participants with history of known allergy to any of the study medication, their analogues, or excipients.
Section 2.5: Study Design Rationale	Deletion of the sentence related to remote site monitoring not available in Germany.	To align with Germany health authority requirements.
Sections 4.1.2: Blinded Treatment Period (Weeks 1 to 25); Section 4.1.3: Open Label Period (Weeks 25 to 53); Section 4.1.4: End of Study Visit (Four Weeks post last dose of study drug); Section 4.1.5: Long Term Extension (LTE); Section	Mean platelet volume has been added to hematology and the word "random" is added for glucose test.	For consistency with the rest of the protocol.
Section 6.1.1: Rilzabrutinib/Placebo	The following text has been added to the section describing the study intervention: "Each tablet is coated with a light orange film coat (Opadry II 85F130006) containing polyvinyl alcohol, polyethylene glycol, talc, titanium dioxide, and FD&C yellow #6."	To provide additional information on excipients.
Section 9.3.9.5: Pregnancy	In the following sentences the word "will/should" has been replaced with "must": "Any female participant who becomes pregnant while participating in the study must discontinue study intervention or be withdrawn from the study."	To ensure participant's safety and to comply with regulatory guidance.
Section 9.3.9.6: Adverse Events of Special Interest	"In the event of pregnancy in a female participant, IMP must be discontinued"	
Section 12.2: Informed Consent	The following statement has been added to the section about signing a specific informed consent form (ICF) for female partners: "for male participants, in case of pregnancy of your partner, your partner will be asked to provide consent for collection of the pregnancy data."	To provide information on signing a specific ICF for the partners of the male participants.
Section 16 Appendix 8: Guidelines to Sites for Delayed Participant Visits or Missed Visits due to travel restrictions and any foreseeable impacts of COVID-19	Cross-references referring to Appendix 10.2 and Appendix 10.7 have been added. Deletion of the sentence related to remote site monitoring not available in Germany.	As per addition of text in Appendix 10.2 and Appendix 10.7. To align with Germany health authority requirements.

Section # and Name	Description of Change	Brief Rationale
Section 16 Appendix 10: Country-Specific Requirements, 10.2 Germany country-specific requirements.	Deletion of the text: "Section 2.5, Study design rationale; Appendix 8, Remote site monitoring: During the coronavirus (COVID-19) pandemic, remote site monitoring is not available in Germany" Added the following text: "Direct to participant shipment is only allowed until 31 December 2023, as long as the ordinance "Ordinance to ensure the supply of medically necessary products to the population in the event of an epidemic caused by the SARS-CoV-2 Coronavirus (Ordinance to Ensure the Supply of Medicines)" is in place in Germany."	To align with Germany health authority requirements.
Section 16 Appendix 10: Country-Specific Requirements, 10.6 Italy country-specific requirement	Added the following text: "For the pediatric population, Tanner staging should be performed at W1, W25, W53, end of study (EOS)/early termination (ET), and every 1 year during the LTE period until the end of the trial or until the participant reaches Tanner stage V (whichever comes first). Self-reported Tanner staging or records from pediatric assessments in standard-of-care settings are considered acceptable." Included the following statement: "Details regarding risk mitigation measures for exceeding blood sample volumes are provided in the Laboratory Manual."	Health authority requirement to assess pubertal status in adolescent participants. To provide information on risk mitigation measures for exceeding blood sample volumes
Section 16 Appendix 10: Country-Specific Requirements, 10.7 EU (EEA countries) and UK-specific requirements	Deleted the word "adult" Sub-section: EU (EEA countries) only, added contingency measures for the COVID-19 pandemic.	Correction and consistency To provide additional information on contingency measures and data management during the pandemic.
Section 16 Appendix 11: Protocol Amendment History	Added the summary of changes from the prior amendment.	To comply with the Sanofi template.
Section 16 Appendix 12.1 Definition of AE, Events meeting the AE definition	Added the following to the lists of events meeting an adverse event (AE) criterion: "Signs, symptoms, or the clinical sequelae of any medication errors, misuse and abuse with the investigational medicinal product (IMP). An abuse corresponds to the persistent or sporadic, intentional excessive use of a medicinal product, which is accompanied by harmful physical or psychological effects, ie, intentional non-therapeutic use of a medicinal product by a participant for a perceived reward or desired non-therapeutic effect including, but not limited to, "getting high" (euphoria)."	To comply with the Sanofi template.

In addition, other minor editorial changes (eg, grammatical, stylistic, abbreviations, references, and minor typographical error corrections) were implemented throughout the protocol.

Appendix 12 AE and SAEs: Definitions and procedures for Recording evaluating, Follow-up, and Reporting

Appendix 12.1 Definition of AE

AE definition

- An AE is any untoward medical occurrence in a patient or clinical study participant, temporally associated with the use of study intervention, whether or not considered related to the study intervention.
- NOTE: An AE can therefore be any unfavorable and unintended sign (including an abnormal laboratory finding), symptom, or disease (new or exacerbated) temporally associated with the use of study intervention.

Definition of unsolicited and solicited AE

- An unsolicited AE is an AE that was not solicited using a participant diary and that is communicated by a participant/LAR who has signed the informed consent. Unsolicited AEs include serious and non-serious AEs.
- Potential unsolicited AEs may be medically attended (ie, symptoms or illnesses requiring a hospitalisation, or emergency room visit, or visit to/by a health care provider). The participants/LAR will be instructed to contact the site as soon as possible to report medically attended event(s), as well as any events that, though not medically attended, are of participant's/LAR's concern. Detailed information about reported unsolicited AEs will be collected by qualified site personnel and documented in the participant's records.
- Unsolicited AEs that are not medically attended nor perceived as a concern by participants/LARs will be collected during interview with the participants/LARs and by review of available medical records at the next visit.
- Solicited AEs are predefined local and systemic events for which the participant is specifically questioned, and which are noted by the participants in their diary.

Events meeting the AE definition

- Any abnormal laboratory test results (hematology, clinical chemistry, or urinalysis) or other safety assessments (eg, ECG, radiological scans, vital signs measurements), including those that worsen from baseline, considered clinically significant in the medical and scientific judgment of the Investigator (ie, not related to progression of underlying disease), eg:
 - Symptomatic and/or
 - Requiring either corrective treatment or consultation, and/or
 - Leading to IMP discontinuation or modification of dosing, and/or
 - Fulfilling a seriousness criterion, and/or
 - Defined as an AESI

- Exacerbation of a chronic or intermittent pre-existing condition including either an increase in frequency and/or intensity of the condition.
- New conditions detected or diagnosed after study intervention administration even though it may have been present before the start of the study.
- Signs, symptoms, or the clinical sequelae of a suspected drug-drug interaction.
- Signs, symptoms, or the clinical sequelae of a suspected overdose of either study intervention or a concomitant medication.
- Signs, symptoms, or the clinical sequelae of any medication errors, misuse, and abuse with the IMP. An abuse corresponds to the persistent or sporadic, intentional excessive use of a medicinal product, which is accompanied by harmful physical or psychological effects, ie, intentional non-therapeutic use of a medicinal product by a participant for a perceived reward or desired non-therapeutic effect including, but not limited to, “getting high” (euphoria).
- “Lack of efficacy” or “failure of expected pharmacological action” per se will not be reported as an AE or SAE. Such instances will be captured in the efficacy assessments. However, the signs, symptoms, and/or clinical sequelae resulting from lack of efficacy will be reported as AE or SAE if they fulfill the definition of an AE or SAE.
- The signs, symptoms, and/or clinical sequelae resulting from lack of efficacy will be reported as AE or SAE if they fulfill the definition of an AE or SAE. Also, “lack of efficacy” or “failure of expected pharmacological action” also constitutes an AE or SAE.

Events NOT meeting the AE definition

- Any clinically significant abnormal laboratory findings or other abnormal safety assessments which are associated with the underlying disease, unless judged by the Investigator to be more severe than expected for the participant’s condition.
- The disease/disorder being studied or expected progression, signs, or symptoms of the disease/disorder being studied, unless more severe than expected for the participant’s condition.
- Medical or surgical procedure (eg, endoscopy, appendectomy): the condition that leads to the procedure is the AE.
- Situations in which an untoward medical occurrence did not occur (social and/or convenience admission to a hospital).
- Anticipated day-to-day fluctuations of pre-existing disease(s) or condition(s) present or detected at the start of the study that do not worsen.

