9.3.2. Adverse Events

An AE is any untoward medical occurrence in a participant or clinical investigation participant administered a pharmaceutical product and which does not necessarily have to have a causal relationship with the intervention. An AE can therefore be any unfavorable and unintended sign (including an abnormal laboratory finding, for example), symptom, or disease temporally associated with the use of an IMP, whether or not considered related to the product. All AEs encountered during the clinical study will be reported in detail in the source documents and documented in the eCRF, from the date of participant consent throughout the follow-up visit. Pre-existing conditions that worsen during a study are to be reported as AEs, with the exception of expected variation in ITP disease activity itself.

Unexpected progression, signs, or symptoms of the disease under study (ITP) are not AEs and are not to be recorded on the AE page of the eCRF unless the event meets the definition of an SAE or is not consistent with the typical clinical course of the participant's disease as established by the participant's medical history. Worsening of the disease under study or other disease-related symptoms should be recorded as an AE only if the event meets the definition of an SAE or is not consistent with the typical clinical course of the disease.

Definitions:

The below guidelines should be followed when recording AEs:

- Medical terms: Whenever possible, use recognized medical terms when recording AEs on the AE eCRF. Do not use colloquialisms or abbreviations.
- Diagnosis: If known or suspected, record the diagnosis (except for eg, hypoglycemia) rather than component signs and symptoms on the AE eCRF and SAE form (eg, record congestive heart failure rather than dyspnea, rales, and cyanosis.) However, signs and symptoms that are considered unrelated to an encountered syndrome or disease should be recorded as individual AEs on the AE eCRF and SAE form.
- Death: Death is an outcome of an event. The event that resulted in the death should be recorded and reported on the AE eCRF and SAE form (except for sudden, unexplained death).

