#### **1.2.2.3.2 Safety Endpoints**

- Frequency and severity of treatment-emergent adverse events (TEAEs).
- Frequency and severity of bleeding TEAEs.
- Change from baseline in physical examination, electrocardiogram (ECG), vital signs and clinical laboratory test results: serum chemistry and hematology (except for platelet counts included in the primary efficacy endpoint).

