## 3.4 TERTIARY/EXPLORATORY ENDPOINT(S) ANALYSIS

### 3.4.1 Definition of endpoint(s)

Please see [Section 1.2.2.4.1](#) and [Section 1.2.2.4.2](#).

Additional details are provided for specific exploratory efficacy endpoints below. Details of COA related endpoints could be found in [Section 3.7.3](#).

*Proportion of participants able to achieve platelet counts  $\geq 50,000/\mu\text{L}$  for 4 out of last 8 weeks of the 24-week treatment period*

Refer to [Section 3.2.1](#).

*Percentage of weeks with platelet count  $\geq 50,000/\mu\text{L}$  OR between  $\geq 30,000/\mu\text{L}$  and  $< 50,000/\mu\text{L}$  and at least doubled from baseline over the 24-week blinded treatment period in the absence of rescue therapy*

Refer to [Section 3.3.1.1](#). For each participant, percentage will be based on the available number of weeks with platelet counts including the weeks censored due to rescue therapy during the double-blind period.

*Proportion of participants with complete response (defined as platelet count  $\geq 100,000/\mu\text{L}$  on 2 consecutive visits at least 5 days apart and no bleeding or rescue ITP therapy use on and through these two visits.*

To qualify for a complete responder, a participant must have met ALL of the following criteria:

- Platelet counts  $\geq 100,000/\mu\text{L}$  on 2 consecutive visits at least 5 days apart, any time from Week 2 to Week 25 and
- No bleeding on and through these two visits (ie, bleeding events identified by SMQ = Haemorrhages via broad and narrow search in eCRF “Adverse Events”);
- Not rescued within the 4 weeks prior to the elevated platelet count and on and through these two visits.

*Proportion of participants with platelet count  $\geq 50,000/\mu\text{L}$  on 2 consecutive visits at least 5 days apart and no rescue ITP therapy use on and through these two visits.*

To qualify for a responder, a participant must have met ALL of the following criteria:

- Platelet counts  $\geq 50,000/\mu\text{L}$  on 2 consecutive visits at least 5 days apart, any time from Week 2 to Week 25 and

- Not rescued within the 4 weeks prior to the elevated platelet count ([Section 3.3.1.1](#)) and on and through these two visits.

*Proportion of participants who have a platelet count that exceeds 250,000/ $\mu$ L or 450,000/ $\mu$ L (for participants on TPO-RA)*

To qualify for a responder, a participant must have met ALL of the following criteria:

- Concomitantly on TPO-RA;

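### Protocol Appendix 12.1 says both that lack of efficacy is not an AE and that it is, and conflicts with Section 9.3.2 on ITP signs, so TEAE and bleeding-TEAE summaries may be distorted

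*Protocol*

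**What the plan says.** **Lack of efficacy.** Two adjacent bullets in Protocol Appendix 12.1, under the events that meet the AE definition, address it. The first says that lack of efficacy "per se will not be reported as an AE or SAE" and is captured in the efficacy assessments. The second ends: "Also, “lack of efficacy” or “failure of expected pharmacological action” also constitutes an AE or SAE". On consequences the two agree: signs, symptoms or "clinical sequelae resulting from lack of efficacy will be reported as AE or SAE if they fulfill the definition of an AE or SAE".

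**Signs of ITP.** Protocol Section 9.3.2 states: "Unexpected progression, signs, or symptoms of the disease under study (ITP) are not AEs and are not to be recorded on the AE page". An exception follows for events that are serious or that depart from the participant's typical course. The same wording returns in that section's bullet on the disease under study. Appendix 12.1, under events that do not meet the definition, excludes instead "expected progression, signs, or symptoms of the disease/disorder being studied, unless more severe than expected" for the participant's condition.

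**Where the AE page is used.** The safety endpoints include "Frequency and severity of bleeding TEAEs" (SAP 1.2.2.3.2), which SAP Table 8 selects by a MedDRA haemorrhage query. SAP Table 7 tabulates all TEAEs and TEAEs leading to permanent discontinuation. Exploratory complete response also draws on the AE page: "No bleeding on and through these two visits (ie, bleeding events identified by SMQ = Haemorrhages via broad and narrow search" (SAP 3.4.1).

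**The concern.** These are working instructions to about 150 sites. A site cannot follow both bullets on lack of efficacy, and it gets opposite words for which ITP signs to leave off the AE page. All of this stands in the current text, not in the amendment history.

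Recording that varied at random between sites would add noise. Here the recorded item is tied to treatment. The plan expects more non-response on placebo, and SAP 3.2.3.2 expects high dropout particularly in that arm. If some sites log lack of efficacy as an AE, the extra events fall more often on placebo, in both the any-TEAE row and the row for TEAEs leading to discontinuation.

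Bleeding is the event where the exclusion of ITP signs matters most. It is a manifestation of the disease, a named BTK-inhibitor class effect (Protocol 2.7.1.1) and a stated safety endpoint. The safety tables are descriptive and depend on uniform recording. An event that was never recorded cannot be recovered in analysis.

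**Working it through.** **1. Text comparison: lack of efficacy.** The second bullet opens by repeating the rule on signs, symptoms and sequelae from the first. Its only new content is the sentence that contradicts the first bullet. Deleting it therefore loses nothing. The study stopping rules (Protocol 7.6) also refer to disease-related AEs with lack of efficacy in brackets, wording that presumes it can be an AE.

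**2. Text comparison: ITP signs.** Section 9.3.2 first exempts only *expected* variation in ITP activity, then says *unexpected* progression is not an AE unless it departs from the typical course. Unexpected events usually do depart from it, so the exclusion and its exception nearly cancel. Appendix 12.1 excludes *expected* signs. The word in Section 9.3.2 looks like a drafting slip, but it appears twice and sites must act on it.

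**3. Size: lack of efficacy logged as an AE.** The plan gives no figure on this point. The only inputs from the documents are the planning response rates of 25% and 5% (Protocol 10.1), so non-response is 75% on rilzabrutinib and 95% on placebo. As background, exact Fisher power at 129 versus 65 with these rates is 96.4%, in line with the stated 95%.

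Let b be the background any-TEAE rate, equal in both arms; s the share of non-responses logged as an AE; and q the non-response rate. Independence is assumed. Both b and s are assumptions. Then any-TEAE = 1 − (1 − b)(1 − s·q), and rilzabrutinib minus placebo = −(1 − b) × s × 0.20.

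| b | s | Rilzabrutinib | Placebo | Difference (points) |
|---|---|---|---|---|
| 50% | 25% | 59.4% | 61.9% | −2.5 |
| 50% | 50% | 68.8% | 73.8% | −5.0 |
| 50% | 100% | 87.5% | 97.5% | −10.0 |
| 80% | 25% | 83.8% | 84.8% | −1.0 |
| 80% | 50% | 87.5% | 89.5% | −2.0 |
| 80% | 100% | 95.0% | 99.0% | −4.0 |

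Over these ranges the spurious shift is 1 to 10 points, with placebo looking worse. A lower background widens it: at b = 30% and s = 100% it is 14 points.

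**4. Size: typical ITP bleeding left off the page.** Assume true bleeding of 20% on rilzabrutinib and 40% on placebo (not in the documents).
- Half recorded in both arms: 10% versus 20%. The difference falls from 20 to 10 points and the ratio stays 0.50.
- Recorded 75% versus 50%: 15% versus 20%, ratio 0.75.
- Recorded 80% versus 40%: 16% versus 16%, ratio 1.00.

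Step 3 makes placebo look worse; step 4 makes it look better. The documents do not say how far either operates.

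**The case against.** The strongest case on the other side is that the consequences are limited. Most of it stands.

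- **Omission of ITP symptoms.** A reader might infer that sites are told to leave ITP symptoms out altogether. They are not: serious or atypical events are recorded under Section 9.3.2, and sequelae of lack of efficacy that meet the AE definition are recorded under Appendix 12.1.
- **A 20-point excess.** A reader might carry the whole gap between 95% and 75% into the TEAE comparison. That would need no background TEAEs and every non-response logged. Missing durable response is also not lack of efficacy as a site would log it: partial responders miss it, and dropout and missing data count as non-response. The planning rates are only an upper bound.
- **Masking of a drug effect.** TEAEs are shown by SOC and PT, so a lack-of-efficacy term would have its own row. Bleeding, infection and gastrointestinal events are selected by their own queries or terms. Safety is descriptive with no testing (SAP 3.6), and recording is blinded. The primary endpoint treats discontinuation for lack of response and for a related AE alike.
- **Overstated complete response.** This is weakly supported. The endpoint is exploratory and requires counts of at least 100,000/µL at two consecutive visits, where bleeding is least likely to be dismissed as typical ITP.
- **Bleeding is measured elsewhere.** IBLS is summarized at each visit (SAP 3.7.3.1). It helps but does not replace AE recording: clinic visits are four weeks apart, recall is one week, items not done score 0, and SAP Table 11 describes it as considered not validated.

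None of this makes the instructions consistent.

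**Conclusion.** The contradiction is real, sits in operative text and should be corrected. What follows from it is a risk of uneven recording, not a demonstrated bias. Total TEAE counts, TEAEs leading to discontinuation and bleeding-TEAE summaries may be distorted. The net direction and size cannot be derived, because the two mechanisms can act in opposite directions.

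The 1 to 10 points against placebo illustrate the first mechanism only. They rest on the planning rates as an upper bound for logged lack of efficacy, assumed background rates of 50% to 80% and assumed recording shares of 25% to 100%.

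**What to change.** 1. In Appendix 12.1, delete the bullet that says lack of efficacy constitutes an AE or SAE.
2. In Section 9.3.2, change *unexpected* to *expected* in both places, so that one recording rule applies throughout.
3. In the SAP, report any lack-of-efficacy terms already recorded separately from the TEAE totals, and present bleeding TEAEs alongside the IBLS summaries.

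The cost is a protocol clarification or amendment wording and a short SAP edit, with no new data collection. Randomization began on 16 April 2021, so the wording change cannot repair events already recorded or omitted; item 3 deals with the lack-of-efficacy terms already on file.

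Two larger changes are not recommended. Requiring every bleed on the AE page now is a debatable trade-off, because recording would become inconsistent over time. Redefining complete response with IBLS would not work as the schedule stands: IBLS is not done at the weekly laboratory visits and has one-week recall.
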